8.3.3 Regulatory Reporting Requirements for SAEs

Once the Investigator or designee becomes aware that a study participant has experienced an SAE, they or designated study staff must report it to Sponsor's delegate immediately, no later than 24 hours of obtaining knowledge, using an electronic Expedited AE Report in the eCRF. The Investigator will provide an assessment of causality at the time of the initial report, as defined in the [Appendix 3](#). New or updated information will be recorded on the originally completed form with all changes signed and dated by the Investigator and reported to IQVIA within 24 hours. This is essential for meeting GSK legal

obligations and ethical responsibilities for the participant's safety and the safety of a study intervention under clinical investigation.

For COVID-19-related SAEs, reports should be submitted following routine procedures for SAEs. Local regulatory requirements and GSK's policy for the preparation of an Investigator safety report for SUSARs must be followed. These reports will be forwarded to investigators as necessary.

GSK has a legal responsibility to notify both the local regulatory authority and other regulatory agencies about the safety of a study intervention under clinical investigation. GSK and IQVIA will comply with country-specific requirements related to safety reporting to the regulatory authority, IRB, and investigators.

8.3.4 Treatment of Adverse Events

Any medication administered for the treatment of an SAE should be recorded in the Expedited AE Report.

8.3.5 Solicited Adverse Events

The solicited administration site and systemic events that will be collected during the 7-day follow-up period after each administration (ie, from Day 1 to Day 7, from Day 57 to Day 63, and from Day 169 to Day 175) are presented in [Table 17](#).

The intensity of the solicited AEs will be assessed as described in [Table 18](#).

8.3.6 Participant Card

The Investigator or Investigator's designee must provide the participants with a "participant card" containing information about the clinical study. The participants will be instructed to keep the participant card in their possession at all times throughout the study. In an emergency, this card serves to inform the responsible attending physician/family member that the participant is in a clinical study and that relevant information may be obtained by contacting the Investigator or his/her backup.

8.3.7 Medical Device Deficiencies

Some of the comparator control vaccines used in this study are combination products constituted of a biologic product in a medical device (pre-filled syringes). Refer to [Appendix 1](#) for the definition of combination product and medical device deficiency and [Appendix 6](#) for further details.

8.3.7.1 Detection, Follow-up, and Prompt Reporting of Medical Device Deficiency

The Investigator is responsible for the detection, documentation, and prompt reporting of any medical device deficiency occurring during the study to Sponsor or Sponsor's delegate. This applies to any medical device provided for the conduct of the study.

Device deficiencies will be reported to Sponsor or Sponsor's delegate within 24 hours after the Investigator determines that the event meets the protocol definition of a device deficiency.

The Investigator will ensure that follow-up includes any additional investigations to elucidate the nature and/or related of the device deficiency to the incident. Follow-up applies to all participants, including those who discontinue study intervention or the study.

New or updated information will be recorded on the originally completed form with all changes signed and dated by the Investigator and reported to Sponsor or Sponsor's delegate within 24 hours.

Medical device deficiencies and any associated AE/SAEs for associated person (ie, spouse, caregiver, site staff) will also be collected. The associated person will be provided with a safety reporting information and authorization letter.

Follow-up applies to all participants, including those who discontinue study intervention or the study, and associated persons.

8.3.7.2 Regulatory Reporting of Medical Device Deficiency When Used as Combination Product

The Investigator will promptly report all device deficiencies occurring with any medical device provided for use in the study to Sponsor or Sponsor's delegate. Sponsor or Sponsor's delegate has a legal responsibility to notify appropriate regulatory authorities and other entities about safety information linked to medical devices being used in clinical studies.

The Investigator, or responsible person according to local requirements (eg, the head of the medical institution), will comply with the applicable local regulatory requirements relating to the reporting of device deficiencies to the IRB/IEC.

8.4 Pharmacokinetics and Pharmacodynamics

Pharmacokinetics and pharmacodynamic parameters are not evaluated in this study.

8.5 Study Procedures During Special Circumstances

During special circumstances (eg, COVID-19 pandemic), the specific guidance from local public health and other competent authorities regarding the protection of individuals' welfare must be followed. For the duration of such special circumstances, the following measures may be implemented for enrolled participants:

- Safety follow-up may be made by a phone call, other means of virtual contact, or home visit, if appropriate.
- Visits for suspected AEs may take place in a different location* other than the study center or at participant's home. If this is not feasible, then the medical evaluation of AEs may take place through remote visit with documentation of symptoms by other means of communication (eg, phone call or videoconference), if possible. Refer to [Appendix 1](#) for the definition of remote visit.
- Biological samples may be collected at a different location* other than the study center or at participant's home. Biological samples should not be collected if they cannot be processed in a timely manner or appropriately stored until the intended use.
- COVID-19 test will be performed pre and post-study intervention administration on participants with symptoms or clinical suspicion of COVID-19, as per the Investigator's discretion.

*Note: It is the Investigator's responsibility to identify an alternate location. The Investigator should ensure that this alternate location meets ICH GCP requirements, such as adequate facilities to perform study procedures, appropriate training of the staff, and documented delegation of responsibilities in this location. This alternate location may need to be covered by proper insurance for the conduct of study on participants by Investigator and study center staff other than the designated study center.

8.6 Genetic Testing

Based on advice from Belgian CA (FAHMP), to minimize any risk of autoimmune reactions, and spondyloses specifically, blood samples collected for safety during Screening in stage 1 will undergo sampling for HLA-B27 genetic marker and only prospective participants who are found to be negative for HLA-B27 will be included in the study [[McColl, 2000](#); [Ekman, 2000](#); [Zeidler, 2021](#)]. Refer to [Appendix 5](#) for details.

9.0 STATISTICAL CONSIDERATIONS

9.1 Statistical Hypotheses

No formal statistical hypotheses are to be tested.

9.2 Sample Size Determination

A total of 155 participants are planned to be randomized to achieve at least 133 evaluable participants in the Per Protocol analysis set for immunogenicity, assuming a 12% dropout rate for each group. Participants who withdraw from the study will not be replaced.

No confirmatory objectives are planned in this trial; however, the sample size was chosen to allow an exploratory comparison of immunogenicity 28 days after the third administration in Stage 2 (Day 197), between participants receiving full dose of candidate iNTS-TCV vaccine and separate full doses of iNTS-GMMA and TCV vaccines, with respect to Anti-*S. Typhi* Vi Ag total IgG, Anti-*S. Typhimurium* O Ag total IgG, Anti-*S. Enteritidis* O Ag total IgG.

9.3 Populations for Analyses

For purposes of analysis, the analysis sets in [Table 10](#) are defined.

Table 10 Analysis Sets

Analysis Set	Description
Enrolled Set	Participants who were randomized or received study intervention or underwent a post-screening procedure. Note that as per Good Clinical Practice, an enrolled participant should have completed the informed consent process and participants should be eligible before initiating any study procedure. The allocation in a group is based on the administered intervention.
Exposed Set (ES)	All participants who received at least 1 dose of the study intervention. The allocation in a group is based on the administered intervention.
Full Analysis Set (FAS)	All participants who received at least 1 dose of the study intervention and have post-dose immunogenicity data. The allocation in a group is based on the randomized intervention. The FAS for immunogenicity will be defined by time point.
Per Protocol Set (PPS)	All eligible participants who received all doses as per protocol, had immunogenicity results post-dose, complied with dosing/blood draw intervals, without intercurrent conditions that may interfere with immunogenicity and without prohibited concomitant medication/vaccination. The PPS for immunogenicity will be defined by time point.
Unsolicited Safety Set	All participants who received at least 1 dose of the study intervention (ES) that report unsolicited adverse events (AEs)/report not having unsolicited AEs. The allocation in a group is based on the administered intervention.
Solicited Safety Set	All participants who received at least 1 dose of the study intervention (ES) who have solicited safety data. The allocation in a group is based on the administered intervention.

If the participant meets one of the criteria mentioned below or ones listed in the Section [7.2](#), he/she may be eliminated from per protocol analysis.

- Use of any investigational or non-registered product (drug or vaccine) other than the study vaccine(s) used during the study period.
- Use of immunosuppressants or other immune-modifying drugs administered chronically (ie, more than 14 days in total) during the study period. For corticosteroids, this will mean prednisone 20 mg/day (for adult participants), or equivalent. Inhaled and topical steroids are allowed.
- Use of any long-acting immune-modifying drugs administered at any time during the study period (eg, infliximab).
- Use of any vaccine not foreseen by the study protocol administered during the entire period of participant's study participation, with the exception of flu vaccines, COVID-19 vaccines, and vaccines administered routinely according to the national immunization program.
- Use of any Immunoglobulins and/or any blood products administered during the study period.
- Any drug and/or alcohol abuse.
- Occurrence of a condition that has the capability of altering their immune response (ie, varicella) or are confirmed to have an alteration of their initial immune status.
- Occurrence of a serious chronic or progressive disease according to judgment of the Investigator (eg, neoplasm, insulin dependent diabetes, cardiac, renal, or hepatic disease).
- Occurrence of any malignancy or lymphoproliferative disorder.
- Occurrence of any confirmed or suspected immunosuppressive or immunodeficient condition, based on physical examination.
- Unblinding after any study intervention has been performed.
- Other details to be included in the Statistical Analysis Plan.

9.4 Statistical Analyses

The Statistical Analysis Plan will be developed and finalized before database lock and will describe the participant analysis sets to be included in the analyses, and procedures for accounting for missing, unused, and spurious data. This section is a summary of the planned statistical analyses of the primary and secondary endpoints.

9.4.1 Primary Endpoints

The analysis on primary objective will be based on the Solicited, Unsolicited, and Exposed Sets, as indicated in [Table 11](#).

Table 11 Primary Endpoints-Statistical Analyses

Endpoint	Statistical Analysis Methods
Primary safety	
 The number and percentage of participants with at least 1 solicited administration site and systemic event during the 7-day follow-up period will be tabulated by group after each study intervention administration and overall. The same calculations will be performed for symptoms rated as Grade 3. The number and percentage of participants with at least 1 unsolicited adverse event (AE) during the 28-day follow-up period will be tabulated by group after each study intervention administration and overall. The same calculations will be performed for symptoms rated as Grade 3. The percentage of doses associated with at least 1 solicited administration site and systemic event during the 7-day follow-up period will be tabulated for the overall administration course. The same calculations will be performed for symptoms rated as Grade 3. The percentage of doses associated with at least 1 unsolicited AE during the 28-day follow-up period will be tabulated for the overall administration course. The same calculations will be performed for symptoms rated as Grade 3. The number and percentage of participants reporting each individual solicited administration site (ie, injection site pain, erythema [redness], swelling) and systemic event (ie, fever [$\geq 38.0^{\circ}\text{C}$], headache, myalgia, arthralgia, fatigue; any Grade and Grade 3) during the 7-day solicited follow-up period after each study intervention administration and by group will be tabulated. The percentage of doses associated with each individual solicited administration site and systemic event will be tabulated for the overall administration course. Occurrence of fever will be reported as number and percentages of participants reporting temperature $\geq 38^{\circ}\text{C}$ in 0.5°C cumulative increments during the 7-day follow-up period. This will be tabulated for each group after each dose. The number and percentage of participants with at least 1 reported unsolicited AE during the 28-day follow-up period after each study intervention administration and by group, as classified by the Medical Dictionary for Regulatory Activities (MedDRA) preferred term, by system organ class and by group will be tabulated. The same tabulation will be performed for Grade 3 unsolicited AEs and for unsolicited AEs according to relationship to study intervention administration. The number and percentage of participants reporting serious AEs (SAEs) and AEs/SAEs leading to withdrawal from the study and/or withholding doses of study intervention, collected from first study intervention administration up to 28 days after third study intervention administration (Day 1 to Day 197) will be tabulated. The detailed listings will also be produced. For each group, for hematological, renal, and hepatic panel test results at 7 days after each study intervention administration (Day 8, Day 64, and Day 176) and at 28 days after each study intervention administration (Day 29, Day 85, and Day 197), and for other tests at baseline: 
 The percentage of participants having hematological, renal, and hepatic results below or above the laboratory normal ranges will be tabulated by time point.

Endpoint	Statistical Analysis Methods
	
 - The maximum Grade from Day 1 until the end of the participant's participation will be tabulated. 
The verbatim reports of unsolicited symptoms will be reviewed by a physician and the signs and symptoms will be coded according to the MedDRA Dictionary for AE Terminology.

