2.3 Benefit/Risk Assessment

2.3.1 Risk Assessment

During the current trial, there may be risks related to the blood sampling (eg, bruising and pain at the blood draw site).

The iNTS-TCV candidate vaccine is yet to be tested in humans.

Of the 3 iNTS-TCV vaccine components, the BioE-TCV has been licensed in India since January 2020 and WHO Prequalified in December 2020. It was well tolerated during clinical trials in 6-month-old to 64-year-old participants and has a safety profile similar to other injectable vaccines.

The GSK GMMA-technology has been applied to a candidate vaccine against *Shigella Sonnei*. The *S. Sonnei* candidate vaccine 1790GAHB has been tested in two Phase 1, an extension study, Phase 2a and Phase 2b clinical studies and was shown to be immunogenic and well tolerated in healthy European, African, and US adults [Launay, 2017; Launay, 2019; Obiero, 2017; Robert, 2021; Frenck, 2021].

The human data on BioE-TCV and iNTS-GMMA (trials with BioE-TCV and iNTS-GMMA are being conducted in parallel with the current trial), will de-risk the development of the iNTS-TCV candidate vaccine.

CCI

[REDACTED]

CCI

Based on GSK's preclinical data produced with other antigens, co-formulation of GMMA and TCV is unlikely to adversely impact on the antibody response induced by each component.

As for any vaccine administered intramuscularly, local reactions such as injection site pain, injection site redness, and injection site swelling may occur within days after administration. Injection of saline does not usually cause side effects other than the ones known for any injection (eg, local pain, injection site reactions, muscle pain).

More detailed information about the known and expected benefits and risks and reasonably expected AEs related to iNTS-TCV may be found in the current Investigator's Brochure (IB).

Detailed information about the known and expected benefits and risks and expected AEs of Menveo, Boostrix, and Typhoid Vi polysaccharide vaccine (Typhim Vi) can be found in their respective Prescribing Information/Package Insert/ Summary of Product Characteristics (SmPC).

Coronavirus Disease 2019

During special circumstances (eg, coronavirus disease 2019 [COVID-19] pandemic), the specific guidance from local public health and other competent authorities regarding the protection of individuals' welfare must be applied.

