4.0 STUDY DESIGN

4.1 Overall Design

This is a Phase 1/2a, observer-blind, randomized, dose-escalation, controlled, multi-country, two-staged, staggered study including 9 groups.

The full dose of the TCV component is the licensed dose of the TCV vaccine, while the full dose of both iNTS components have been tested in repeat-dose toxicology studies in rabbits and were well tolerated. The details of the selected doses are provided in Section 4.3.

The study will be conducted overall (both Stage 1 and Stage 2) with approximately 155 healthy adult participants (18 to 50 years of age). The healthy European adults will be randomly assigned to 1 of the groups indicated for Stage 1 (refer to Section 4.1.1). The healthy African adults will be randomly assigned to 1 of the groups indicated for Stage 2 (refer to Section 4.1.2).

Each group will receive 2 of the 11 study interventions at each administration, except for the Control_Stage 2 group which will receive 4 study interventions (a different active comparator at each administration time point together with saline) ([Table 4](#)).

Each participant will receive 1 randomly selected intramuscular (IM) study intervention per arm on Day 1, Day 57, and Day 169. Each participant will be part of this trial for approximately 13 months (from the Screening starting 28 days before first study intervention administration and until 6 months after third study intervention administration).

The primary completion date of the study will be at Visit 9 (Day 197), 28 days after the third study intervention. An extended safety follow-up will be performed until 6 months after the third study intervention administration (Day 337) for collection of SAEs.

[Table 1](#) shows the full schedule of activities (SoA) for Stages 1 and 2 and the details of the intervals between study visits are as shown in [Table 2](#).

4.1.1 Stage 1

Stage 1 (Europe) will follow a 2-step staggered design, leading in with low doses of all the study interventions, in a dose-escalation manner. The sentinel approach will be followed for the first 10 participants each in Step 1 and Step 2, in which only 1 participant will be treated daily. This will be done to ensure maximum safety of the participants.

In Step 1, 10 healthy European adults, randomized in a 2:2:1 ratio, will receive:

- The low dose of the candidate iNTS-TCV vaccine and concomitant saline to be administered in different arms, or

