In Stage 2 (Africa), a total of 105 healthy African adults, randomized in a 3:3:1 ratio, will receive:

- The full dose of the candidate iNTS-TCV vaccine and concomitant saline to be administered in different arms, or
- Separate administration of full doses of iNTS-GMMA and TCV vaccines in different arms, or
- MenACWY (Menveo) and saline for the first administration, TdAP (Boostrix) and saline for the second administration and Typhim Vi and saline for the third administration in different arms. This is the Control_Stage 2 group.

The first 21 participants in Stage 2 will initially be recruited with administration proceeding sequentially, at least 60 minutes apart. These participants will be followed up with a safety follow-up call on the next day of administration of study intervention. If the participants have any complaints, they will be invited to the study site for an evaluation of the possible AEs and holding rules, prior to administration of study intervention in the next participant. If the Investigator becomes aware of a holding rule being met, he/she must suspend administration of the study intervention and inform the Sponsor's delegate immediately who will in-turn inform the Sponsor. All safety data from these participants up to 7 days after the first administration of the study intervention will be reviewed by the iSRC and the recruitment of the remaining 84 participants in Stage 2 will only commence if there is a positive evaluation by the iSRC. The study interventions will be administered in parallel in the remaining 84 participants.

All 155 participants (Stage 1 and Stage 2) will be closely observed for a minimum of 60 minutes after each study intervention administration, before leaving the facilities. The Investigator will decide if the participant should be observed for more than 60 minutes after each study intervention administered, if required.

Table 4 Study Groups, Intervention, and Blinding

Study groups			Number of participants	Age (Min-Max)	Study interventions first administration	Study interventions second administration	Study interventions third administration	Blinding Visit 1→Visit 10 (Observer-blind)*	
					iNTS-TCV low dose	iNTS-TCV low dose	iNTS-TCV low dose		
Stage 1 (50 participants)	Step 1 (10 participants)	1	Invasive nontyphoidal Salmonella-typhoid conjugate vaccine (iNTS-TCV) low dose	4	18 – 50 years	Saline	Saline	Saline	X

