16.1. ADVERSE EVENTS

The analysis of solicited adverse event will be performed in the Solicited Safety Set. The percentage of participants with at least 1 administration site AE (solicited and unsolicited), with at least 1 systemic AE (solicited and unsolicited) and with any AE during the 7-day or the 28-day follow-up period, for each stage, will be tabulated with exact 95% CI after each vaccination and overall. The same calculations will be performed for symptoms rated as grade 3 (severe). This combined analysis of solicited and unsolicited AEs will be performed on the Exposed Set as requested for public disclosure. Solicited

Document: \\dccar2dnetvnasc01p-lan1.quintiles.net\cp_ops\PROJECTS\Glaxo SmithKline\GSK216152_WZA10802\SAP
 Author: PPD Version Number: 2.0
 Version Date: 07DEC2023

Template No: CS_TP_BS016 – Revision 7
 Effective Date: 01Nov2021

Reference: CS_WI_BS005

events and unsolicited AEs will be coded by MedDRA.

The percentage of doses followed by at least 1 administration site AE and by at least 1 systemic AE will be tabulated, overall vaccination course, with exact 95% CI. The same computations will be done for Grade 3 AEs, any unsolicited AEs considered related to vaccination, any Grade 3 unsolicited AEs considered related to vaccination and any AEs resulting in a medically attended visit.

The percentage of participants/doses reporting each individual solicited administration site and systemic AE during the 7-day follow-up period will be tabulated with exact 95% CI as follows:

- Over the 3 doses, the percentage of participants with the symptom and its exact 95% CI.
- Over the 3 doses, the percentage of doses with the symptom and its exact 95% CI.
- At each study dose (visit), the percentage of participants with the symptom and its exact 95% CI.

Occurrence of fever within 7 days post vaccination will be reported per grade, per 0.5°C cumulative increments classes as from $\geq 38^{\circ}\text{C}$ as well as the occurrence of fever $>40^{\circ}\text{C}/104^{\circ}\text{F}$.

Solicited events ongoing after the observation period reported by maximum intensity will be left out of summary tables and only reported in solicited AE listings. Any solicited event with onset day greater than solicited period (i.e., 7 days) will be reported as unsolicited AE and will be included in unsolicited summary tables and listings.

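### Solicited local reactions are tabulated per participant although every visit gives two injections in different arms, so the planned tables do not isolate the local reactogenicity of iNTS-TCV

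*Protocol*

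**What the plan says.** Protocol 4.1 sets the injection pattern: "Each participant will receive 1 randomly selected intramuscular (IM) study intervention per arm on Day 1, Day 57, and Day 169". Under 4.1.2 and Table 4, one Stage 2 group receives "The full dose of the candidate iNTS-TCV vaccine and concomitant saline to be administered in different arms" and another "Separate administration of full doses of iNTS-GMMA and TCV vaccines in different arms"; each has 45 participants. The 15 controls receive a licensed vaccine plus saline, and the Stage 1 placebo groups receive placebo plus saline. Tables 6 and 7 give laterality as random.

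The primary objective is the safety and reactogenicity profile of iNTS-TCV. For solicited local events, Protocol 9.4.1 (Table 11) plans "The number and percentage of participants reporting each individual solicited administration site (ie, injection site pain, erythema [redness], swelling" together with systemic events, by group and administration. SAP 16.1 tabulates per participant and per dose, and its per-dose item reads "At each study dose (visit), the percentage of participants with the symptom and its exact 95% CI". A dose is therefore the visit, with both injections taken together.

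The supporting rules carry no index for injection site:
- Protocol Table 17 lists pain, redness and swelling at the administration site without naming an arm.
- Table 18 grades redness and swelling on one greatest diameter.
- SAP 7.1.3 bases the denominator on one occurrence question for local events as a class.
- SAP 7.2.6 classifies the participant by the highest daily recording.

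On saline, Protocol 2.3.1 says it does not usually cause effects "other than the ones known for any injection (eg, local pain, injection site reactions, muscle pain"). Protocol Appendix 3 asks the Investigator to name the responsible intervention, when possible, for unsolicited events only.

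**The concern.** A reader of the study report will take the local reaction rate in the iNTS-TCV group as the local tolerability of the candidate. As planned, that figure is the proportion of participants with a reaction in the vaccine arm, the saline arm or both.

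Two further readings are affected. In the separate-administration group a local reaction may come from iNTS-GMMA or from TCV, and the planned tables do not say which. A descriptive reading of iNTS-TCV beside the separate group sets one active site against two, so part of any difference reflects the number of active sites. Local tolerability by product would be useful for the choice that Protocol 4.2.1 mentions, between developing a trivalent vaccine and a bivalent iNTS-GMMA vaccine.

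**Working it through.** The plan states no figure on this point, so there is none to reproduce. The unit of analysis follows from the text; the sizes below are illustrations.

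**Inputs from the documents:** two injections per visit (Protocol 4.1); 45 participants in each of the two investigational Stage 2 groups (Table 4); local events counted per participant and per visit (Table 11, SAP 16.1); saline can cause local reactions, with no rate given (2.3.1).

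**Assumed inputs:** vaccine-arm rate pv = 0.3 to 0.8; saline-arm rate ps = 0.05 to 0.20; arms independent unless stated.

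**1. Direction, with no assumption on dependence.** The participant-level rate is P(vaccine arm or saline arm) = pv + P(saline arm only). The second term cannot be negative, so the planned rate equals or exceeds the vaccine-arm rate.

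**2. Illustrative size under independence.** The excess is 1 - (1 - pv)(1 - ps) - pv = (1 - pv) x ps.
- Low end: (1 - 0.8) x 0.05 = 0.01, or 0.01 x 45 = 0.45 participants.
- Middle: (1 - 0.5) x 0.10 = 0.05, so 50% would be reported as 55%.
- High end: (1 - 0.3) x 0.20 = 0.14, or 0.14 x 45 = 6.3 participants; 30% would be reported as 44%.

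**3. Effect of within-person correlation.** With correlation r, P(both) = pv x ps + r x sqrt(pv(1 - pv) ps(1 - ps)), and the excess is ps - P(both). For an assumed r = 0.3:
- pv = 0.3, ps = 0.20: P(both) = 0.06 + 0.3 x sqrt(0.21 x 0.16) = 0.115. The excess is 0.085, down from 0.14.
- pv = 0.5, ps = 0.10: P(both) = 0.05 + 0.3 x sqrt(0.25 x 0.09) = 0.095. The excess is 0.005, down from 0.05.

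**4. Separate group.** Suppose 60% of participants report a local reaction. Under independence, 1 - (1 - a)(1 - b) = 0.60 holds for iNTS-GMMA and TCV arm rates (a, b) of (60%, 0%), (50%, 20%), about (37%, 37%), (20%, 50%) and (0%, 60%). The participant-level rate alone cannot choose among them.

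**5. One active site against two.** Suppose every active site reacts at 50% and saline at 10%. The iNTS-TCV group shows 1 - 0.5 x 0.9 = 55% and the separate group 1 - 0.5 x 0.5 = 75%, although reactogenicity per active site is equal.

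**The case against.** The strongest reply is that the endpoint is reported as defined. Protocol section 3 asks for the number of participants with solicited events by study intervention group, and each group's intervention is a pair of injections. For that regimen the per-participant count is valid. Saline is also given with placebo in Stage 1 and with every control vaccine in Stage 2, and Protocol 4.2.1 says it serves comparison as well as blinding. All of this stands. A reader might infer that the primary local rate is wrong or biased; the documents do not support that, because they set no injection-specific target. What the balance does not provide is the candidate's own local rate.

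Second, SAP 16 plans no statistical comparison of safety between groups unless a section says otherwise, and Protocol 4.2.1 justifies the separate group mainly by immunogenicity and interference. This also stands. The one-site-against-two problem therefore affects descriptive reading only, and failing to separate iNTS-GMMA from TCV misses no stated objective.

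Third, a reader might infer that reactions cannot be attributed to a product at all. That goes too far. The diary, eCRF and table shells are not among the documents. Listings of solicited events (SAP 16.1) and of treatment administration (SAP 9) are planned, so attribution may be possible if side is recorded. The limit applies to the planned tables; neither document says that side is collected or uses it.

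Finally, the excess may be small beside sampling error: the exact 95% CI for 22 of 45 runs from about 34% to 64%. Its direction overstates local reactions, which is cautious for safety. Both are fair, but neither shows which arm reacted.

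**Conclusion.** The point holds in a limited form. The planned tables describe the two-injection regimen correctly and, between iNTS-TCV and placebo or control, with equal numbers of injections. They do not isolate local reactions to iNTS-TCV, do not separate iNTS-GMMA from TCV, and give no rule for combining two sites in one participant.

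The direction is certain: the reported iNTS-TCV rate cannot be below the vaccine-arm rate. The size cannot be computed from the documents. The range of 1 to 14 points, about 0.5 to 6 of 45 participants, rests on assumed rates and independent arms. Its upper end pairs the lowest vaccine rate with the highest saline rate, and falls to about 8.5 points at an assumed correlation of 0.3. This is an inexpensive improvement to reporting; it does not correct a defective endpoint.

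**What to change.** - **If side is already captured:** add to SAP 16.1 a descriptive table of pain, redness and swelling by injection, with arm linked to the product given after unblinding. Show iNTS-TCV-arm reactions separately from saline, and give iNTS-GMMA, TCV, placebo and each control vaccine their own rows.
- **If side is not captured:** add a left/right field to the pDiary and eCRF for administrations still to come, and state the limitation for data already recorded. Recording side needs no unblinding.
- **In either case:** keep the per-participant table, and define it in SAP 7.2.6 as the worse of the two sites.

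The cost is a slightly longer diary if the field is new, and one extra table per stage. By-arm data may be incomplete for Stage 1: Protocol Amendment 2 already refers to deviations seen there and SAP version 2.0 is dated 07 December 2023, so a new field cannot recover reactions already recorded.
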